The HIV epidemic has reached a crisis state among Blacks in the United States. Blacks or African Americans account for approximately half of new HIV diagnoses annually, and the rate of new HIV infections among Black men is about six times that of white men (CDC 2011). The Centers for Disease Control and Prevention estimates that one in sixteen Black men will be diagnosed with HIV in their lifetime (MMWR 2010); this is reflected in the fact that black males have the highest HIV diagnosis rate across all race and sex categorizations (MMWR 2011). Further, among men diagnosed with HIV infection from 2005-2008, 71% of heterosexual transmissions occurred among those identifying as Black, and nearly one quarter of HIV transmissions in Black men are classified as being accounted for by heterosexual contact (MMWR 2011). Although a number of interventions have been developed to address Black priority populations such as youth, heterosexual women, and targeted populations such as drug users and serodiscordant couples, a large gap exists between the HIV prevention needs of adult heterosexual Black men and community-based programs that have been demonstrated as effective in meeting these needs.

Investigators at SUNY Downstate Medical Center and the Arthur Ashe Institute for Urban Health, Inc. have over ten years experience working together on local community based health education initiatives, behavioral interventions, and action oriented projects. More recently, the investigative team involved in this partnership has utilized community-engaged research methods to develop an intervention that seeks to reduce sexual risk behavior among Black adult heterosexual men who do not inject drugs, and which seeks to address contextual-level factors that impacts community risk. The structure for the intervention is theoretically-based, with content informed by our community advisory group, formative data collection, and feedback derived from pilot testing. The goal of this proposal is to test the efficacy of this HIV prevention program among 875 adult, heterosexual Black men. *A cluster randomized trial design will be utilized, with men recruited from barbershops in Brooklyn, NY; therefore barbershops, and not individual men, will be randomized to be a site for intervention activities, or a control site.* These barbershops are located in neighborhoods with high prevalence of HIV infection. Men will complete audio computer assisted structured interviewers (ACASI) at baseline and at three and six months following receipt of our HIV prevention program. The intervention is

consistent with the FY 2011 Trans-NIH Plan for HIV-Related Research, which has as a priority the reduction of HIV-related disparities in racial and ethnic populations, and addresses the needs of a population who bear a disproportionate burden of HIV/AIDS in the U.S., and for whom there are few effective approaches available. A critically important public health challenge is to design acceptable, sustainable HIV prevention programs that can effectively reach and serve high-risk adult heterosexual Black; the results of this study will lay the groundwork toward implementation of effective HIV prevention in this group, and will contribute to our understanding of factors that can support approaches toward behavior change and maintenance in this population.

Aims and Hypotheses:

Aim 1: To assess the impact of a linguistically and culturally tailored HIV prevention program on the HIV risk of heterosexual, African American adult men.

Hypothesis 1: Compared to men assigned to an attention control condition, those exposed to the intervention will have lower levels of sexual risk behavior at a 3 and 6 month follow-up.

Hypothesis 2: Compared to men assigned to an attention control condition, those exposed to the intervention will have improved outcomes at 3 and 6 months, on theoretically derived mediators of sexual risk behavior, including interpersonal factors such as attitudes, self-efficacy, communication skills and perceived norms around safer behavior, as well as on factors such as increased individual and community empowerment and decreased HIV-related stigma.

Aim 2: To examine individual and contextual-level factors that explain variation in the efficacy of the intervention.

Hypothesis 3: Intervention impact will be moderated by individual and contextual level-factors such as higher perceived basic needs and housing instability, incarceration and substance use history, higher perceived racism, and traditional gender role norms and attitudes, such that intervention effects will be reduced among men with these risk factors.

Project Rationale:

Blacks accounted for half (50.3%) of the HIV diagnoses in adolescents and adults in 37 states during 2005—2008 (MMWR 2011). During this time, 56.1% of HIV diagnoses were among persons aged 25-44 years; in this age group, blacks accounted for 46.4% of HIV diagnoses (MMWR 2011). In 2008, among males and females of all racial/ethnic populations, black males had the highest HIV diagnosis rate (131.9 per 100,000) (CDC 2011), and it is expected that 1 in 16 Black men will be diagnosed with HIV in their lifetime (MMWR 2010). Further, while trends in HIV diagnoses reveal relatively stable rates of HIV diagnoses by racial/ethnic and sex group, these rates continue to increase among Black men (MMWR 2011). Nearly a quarter (23%) of HIV transmissions in black males are classified as being accounted for by heterosexual contact (MMWR 2011). There have been significant contributions to our understanding of the predictors of HIV risk among African Americans as it relates to populations of injection drug users and men who have sex with men. There have also been impressive inroads made into understanding factors related to Black women's heterosexual risk behavior and the behaviors of youth. Significantly less is known, however, about how to address the risk behaviors of heterosexual African American adult men and about the individual and contextual factors that put these men at risk for HIV infection. As such, there is a large and unacceptable gap between the prevention needs of these men and the number and quality of prevention programs demonstrated to meet these needs. Despite the need for effective risk reduction approaches, few resources exist to help reduce HIV/AIDS risk among African-American heterosexual men who do not inject drugs and who are at risk primarily due to unprotected sex with multiple or concurrent sex partners of the opposite sex. In response to this need, our investigative team has spent the last several years conducting community-based, formative research in the service of intervention development with and for heterosexually-active African-American men recruited from barbershops located in urban, low-income areas with high HIV morbidity and mortality. In this proposal, we seek to examine the effectiveness of this program, *Barbershop Talk*.

Methods

The *Barbershop Talk* intervention program.

The purpose of this study is to test the efficacy of the *Barbershop Talk* program. Clients who are eligible and who consent to participating in the intervention and corresponding evaluation will engage in the program, which takes approximately up to two hours to complete. The session is broken down into three parts, which are called “wake up”, “gear up”, and “stand up”. In the “wake up” module, participants are oriented to the program objectives and ground rules for the program, and discuss the theme of the module, which is to wake up to the “fire” of local community health problems; this metaphor seeks to demonstrate to men how their natural inclination to take care of others (i.e., how they would react if they witnessed a fire on their block) can be applied in the service of other, less visible problems. During this module, participants engage in discussions of how they see health and what it means to be a healthy man in our society, and an exploration of how definitions and conceptualizations of masculinity impact men’s health behaviors. Discussions of health also focus on social health and networks, and how men can comfortably work within their networks to improve community health. The overall purpose of this first module is to promote community engagement and motivation to engaging in health promotion with men and women in the participant’s social network. During this module we discuss input that we received from our formative work regarding men’s ability and motivation to address health, and discuss a movement in Brooklyn toward control of our own health. The “gear up” module introduces another “fire” – that of HIV. This module utilizes methodologies that have been shown to be standard components of effective HIV interventions, but that are grounded in our formative research and which speak specifically to local concerns and beliefs surrounding condom use, HIV testing, and HIV transmission. These methodologies including educational information, and attitudinal arguments meant to promote positive attitudes toward safer sex and HIV testing, and behavioral skills surrounding condom use (Albarracin, Gillette et al. 2005). This module addresses the local epidemiology of HIV/AIDS, highlighting the burden of heterosexually transmitted infection in the area, includes a discussion about the role of community stigma as a barrier to effectively battling HIV/AIDS, involves a discussion and demonstration surrounding which types of condoms to use and how to use them properly, and includes a myths and truths discussion, in which we address population specific beliefs that came up during the formative work (e.g., anal sex between men and women does not convey risk of HIV transmission; all heterosexual transmissions are the result of men lying about their actual drug use or same sex behavior; a ‘quickie’ without a condom does not put you at risk for HIV, women have physical characteristics that allow you to ‘see’ their HIV status). As part of this module, and congruent with social cognitive theory, men are asked to develop and commit to a step toward behavioral change that they could take to reduce their risk of HIV or that could help reduce risk for someone they know. The third module, “gear up” is about preparing to take what was learned in the intervention and sharing it with sexual partners and others in the participant’s social network. This component of the intervention focuses on developing skills in communicating effectively with sexual partners and with others in the community about HIV risk and protection and the development of a social action plan by which to assist others in learning the information conveyed in the intervention. The majority of the time spent in this last module focuses on developing ‘conversation skills’ around HIV, in which we provide feedback and exercises on ways to communicate effectively. This component spends most of its time working through a number of role play scenarios, which were based on stories of risk that were presented during our formative work. These involve varied physical and emotional contexts of risk, including sexual risk as a function of emotional motivations (anger, loneliness), high risk interactions (sexual pressures from female partners to not use condoms, a theme which came up frequently in our formative work), and high risk settings (when there is limited perceived ‘time’ or ‘opportunity’ to have sex, in clubs, etc.). Participants will be provided \$20 to complete the *Barbershop Talk* program; the program takes about two hours to complete.

Study design and sample size:

The *Barbershop Talk* program will recruit from barbershops, and seeks to leverage the naturally occurring social bonds and networks within barbershops to effect change in HIV-related risk behavior. Although the unit of analysis for the program evaluation is at the individual level, the focus on social relationships and empowerment approaches to building community capacity in the intervention make randomization at the individual level challenging. The nature of our program is such that we seek for participants to reach out within networks to discuss HIV, and barbershop-linked networks of friends and neighbors would be a naturally occurring social network. There exists, therefore, a risk for contamination between intervention and control participants who are recruited within individual barbershops. In order to minimize this risk, we have chosen to use barbershops as the unit of randomization. Program staff will conduct observations of shops and interviews

with staff in order to assess these conditions. Participating barbershops will know in advance of agreeing to work with us that clients will be eligible to receive some form of health education, but that the process of deciding which intervention takes place in the shop is determined via a process of random assignment. We will work with shops to develop a memorandum of agreement in order to establish clear expectations of what will happen in each shop. Shops will be randomized after our list of eligible barbershops is compiled.

The sample size calculation is based on the expected percent of men engaging in high risk behavior after 6 months of follow-up, accounting for the intraclass correlation coefficient (ICC) and estimates of unprotected sex estimated from our pilot dataset of 105 participants from four barbershops. Unprotected sex, defined in this example as two or more sexual partners in the past three months plus at least one episode of unprotected vaginal or anal sex, was reported by 42% of our sample in a previous pilot study of the program. Assuming that 42% of the participants in the control group would engage in high risk behavior, an ICC of 0.03, and a minimum of 23 participants from each barbershop, the study has 80% power to detect an absolute reduction of 12% (relative reduction of 29%) in rates between the two groups with alpha=0.05, two-tailed and 15 barbershops for each intervention group (i.e., 30 clusters and 690 total participants). In order to achieve a sample size of 690 at the six-month follow-up, we estimate that we will need to recruit 875 men in order to account for a loss to follow-up as high as 20%.

Participants:

Inclusion criteria include men age 18 or older who report two or more partners in the past six months, unprotected sex with a woman in the past six months, and identify as Black or African American. Exclusion criteria for participation include (1) having been in an HIV prevention research study in the last six months, (2) reporting a history in the past five years of injection drug use, (3) reporting a history in the past five years of having sex with other men, (4) reporting an HIV-positive serostatus, or (5) inability to understand spoken English. In order to ensure that our program meets the needs of a unique and understudied population, we have chosen to exclude men with an injection drug use history or who report same sex behavior, given that interventions have been developed for these populations and that the behavioral risk and determinants of risk are unique to these subpopulations. However, it is recognized that the very nature of being on the 'down low' would necessitate that some men who engage in same-sex relationships may not report this behavior and be included in the sample. Similarly, the stigmatized nature of injection drug use may be linked to underreporting during our screening and evaluation procedures. The risk in this scenario is that inclusion of men who for whom intervention messages are not tailored could dilute differences between the experimental and control group, but would not cause harm. We note that although we focus on men who identify as Black, some men will also report Latino ethnicity; these men will not be excluded from the study, as reflected in our planned enrollment table. However, given that our program is being completed in barbershops serving African American men, the vast majority of potential enrollees will be English-speaking. During a pilot test of the Barbershop Talk program, we found that of over 100 men who completed a screener, all were able to understand English. While this does not negate the fact that some non-English speaking men may have been less likely to agree to screener, it does speak to the project team's view that translation of all intervention sessions and evaluation measures would not be a worthwhile use of funds given that we are unlikely to be able to have a large enough number of non-English speakers in the sample to be able to draw conclusions about effectiveness in these sub-groups, and that the program was not tailored to what are likely the unique needs of men who are non-English speaking.

Recruitment procedures:

Recruitment will take place in barbershops. Customers will be introduced to study staff by their barber and asked whether they would be willing to meet with our research assistant to complete screening for the study. Given that we will be attempting to enroll all eligible customers within a recruitment period, we anticipate that enrollment at each barbershop will be approximately proportional to the size of that venue's total client pool. The research assistant will describe the study, and assess eligibility via an ACASI screening form with a privacy screen attached. All eligible participants who are interested in participating will provide individual, written, informed consent written at a level appropriate to our priority population. After receiving the information on the Consent Form appropriate for the barbershop condition, the potential participant can direct any additional questions or clarifications to the research assistant. Those who agree to join the study will sign the consent form and will be given a copy for their records, and will complete a locator form. Following the consent

procedure the participant will complete an ACASI administered baseline assessment, and will be provided study activities congruent with the experimental arm assigned at that barbershop. To reduce self-report bias, project staff responsible for recruiting and administering evaluation assessments do not administer intervention activities, and staff administering intervention activities do not administer assessments to those clients. The consent form is written at a Flesch-Kincaid grade level below 8.0.

Program Evaluation:

Audio Computer-Assisted Self-Interview (ACASI) will be utilized to collect self-reported data at baseline (pre-intervention) and also at 3- and 6-month follow-up from the date of completion of the *Barbershop Talk* program. Respondents will listen to headphones and questions will be provided by a recorded voice stored in computer memory. The responses will be entered by pressing on the computer's touchscreen. A privacy screen will be utilized so that other barbershop customers cannot view responses, and headphones with disposable covers will be used so that respondents can listen to questions and answer options. Prior to baseline questions being administered, participants will complete a series of 'warm up' practice items. During our formative work, we piloted the recruitment, screening, consent and baseline procedures described in this project on 78 men and have found them to be feasible to implement, acceptable to barbershop personnel and clients, and a sound method for maintaining privacy and confidentiality. Additionally, at the 6-month interview participants will be asked to complete an additional set of questions to help identify the need for future programs. These final questions will be administered by a study staff in an interviewer led format. Questions 1-3 of the questionnaire pertain to existing knowledge about PrEP, and interest to receive more information about PrEP. In conjunction with these questions, study participants will be offered a PrEP brochure to increase their knowledge about HIV prevention. For question #4 of the interview a response card will be handed to study participants to facilitate the selection of their answers to that question. Participants will be reimbursed at \$20 for the baseline interview, \$30 for the three month follow-up assessment, and \$40 for the six month follow-up assessment, which is reasonable considering the length of the interview, and is in line with typical reimbursement levels for other HIV prevention program evaluations. The evaluation instruments will take approximately forty minutes to complete. All measures described in the following section have been selected based on their established reliability and validity in published HIV prevention studies and with adult African American populations.

All measures included in the program evaluation have been selected based on their demonstrated reliability and validity in published research and in our own previous work in populations similar to the men in this study; we will pilot the instrument prior to administration. To examine hypothesis 1, our main outcome measure will be a composite measure of the proportion of respondents who report two or more partners in the last six months and report unprotected sex during this time. This outcome, which was reported by over 40% of our population in our formative work, is a more informative marker of risk than some other outcome measures used in HIV prevention trials (e.g., any unprotected vaginal or anal sex) in that it helps to differentiate persons engaging in unprotected sex in the context of a single monogamous partnership, versus those who are at higher risk for HIV infection. Other measures of risk will include (1) partner concurrency, (2) number of sexual partners, (3) condom use consistency, and HIV testing. Behaviors will be assessed over the previous three months. Of course, self-report measures of sexual risk behavior are prone to self-report bias as individuals are likely to inflate or deflate their responses based on factors such as gender norms around sexual behavior. However, we will engage in a number of activities to promote honesty in responses by (1) assuring men of the confidentiality of their responses and explain the system that will be used to ensure this, (2) stressing the importance of honest answers to the scientific integrity of the project and for informing community health, (3) and using ACASI. Responses on this measure will be correlated with measures such as sexual behavior and drug use to provide an estimate of the extent to which this bias contributes to scores. Often, clinic-based interventions are able to collect data on more 'hard' outcomes, such as STD rates. The ability to power these studies is based on the fact that participants at baseline typically have and are treated for STD, and that there are known and substantial risks for 'repeat' infections in the control group. In our study, however, it would neither be feasible to conduct STD testing, nor acceptable to do so in the context of a community-based study involving barbershops. As described in our second hypothesis, our intervention is designed to directly influence a set of theoretically derived variables, which in turn are expected to influence sexual risk. These mediating variables include intrapersonal variables such as condom use and HIV testing attitudes, self-efficacy, and subjective norms, as well as perceived skills in communication and negotiation skills around safer sex. These measures are typically ordinal in nature but analyzed as having interval level properties measures

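### The sample-size paragraph claims 80% power, but its own inputs give about 73%

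*Protocol*

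**What the plan says.** The protocol's section *Study design and sample size* holds the only power statement in the two documents; the SAP has none. It starts from the control rate ("Assuming that 42% of the participants in the control group would engage in high risk behavior"), adds the clustering assumptions ("an ICC of 0.03, and a minimum of 23 participants from each barbershop") and concludes that "the study has 80% power to detect an absolute reduction of 12% (relative reduction of 29%) in rates between the two groups". The test and the number of clusters are given as "alpha=0.05, two-tailed and 15 barbershops for each intervention group (i.e., 30 clusters and 690 total participants". Recruitment is then raised for attrition: "we will need to recruit 875 men in order to account for a loss to follow-up as high as 20" per cent. No formula, software, gain from baseline adjustment or allowance for unequal shop sizes is mentioned. The section *Recruitment procedures* expects shop sizes to differ: "enrollment at each barbershop will be approximately proportional to the size of that" venue's client pool.

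**The concern.** Every quantity needed to recompute the power is printed, so the 80% can be checked directly, and the standard calculation for a cluster-randomised comparison of two proportions falls seven to eight points short of it. If the stated inputs are right, the risk of missing a true 12-point reduction is about a third higher than planned. A non-significant result would then be read as stronger evidence against a 12-point effect than the design supports.

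**Working it through.** **Inputs**, all from *Study design and sample size*: control rate p1 = 0.42; reduction 0.12, so p2 = 0.30 (0.12/0.42 = 28.6%, matching the stated 29%); ICC = 0.03; m = 23 men per shop; k = 15 shops per arm; alpha = 0.05 two-tailed; 690 men analysed at six months.

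**Stated power: 80%. Recomputed:**

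1. Men per arm: 15 × 23 = 345; total 690, as stated.
2. Design effect: 1 + (m − 1) × ICC = 1 + 22 × 0.03 = 1.66.
3. Effective men per arm: 345/1.66 = 207.8.
4. Standard error (unpooled): √[(0.42 × 0.58 + 0.30 × 0.70)/207.8] = 0.0467.
5. Standardised difference: 0.12/0.0467 = 2.568.
6. Power: Φ(2.568 − 1.960) = **72.9%**.

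**Other methods at the same inputs**

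| Method | Power |
|---|---|
| Pooled variance under the null | 72.3% |
| Arcsine | 72.5% |
| Log-odds | 71.9% |
| Beta-binomial simulation, 40,000 replicates, shop-level z test | 72.3% |
| t reference, 28 between-shop df (unpooled; pooled) | 69.8%; 69.2% |
| Constant coefficient of variation of shop rates across arms | 75.5–76.3% |

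The documents do not choose a 28-df reference; that row is a sensitivity figure.

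**Does recruitment close the gap?** The attrition step itself is sound: 690/0.80 = 863, and 875 × 0.80 = 700. With 700 analysed men there are 700/30 = 23.3 per shop, the design effect is 1.67, and power is 73.2% unpooled or 72.7% pooled. Even with no loss at all, 875 men (29.2 per shop) give 78.3% or 77.9%.

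**What would give 80% for a 12-point difference** (unpooled to pooled, changing one input at a time):

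- ICC of 0.0180 to 0.0173;
- 31.6 to 32.3 analysed men in each of 30 shops, about 950–970 in total;
- 18 shops of 23 per arm (80.3% unpooled, 79.9% pooled) or 19 (82.4%, 82.0%);
- a one-sided 0.05 test (82.2%, 81.9%).

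Each of these departs from the stated inputs. The documents do not show which, if any, lies behind the 80%.

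**Detectable difference with 80% power at the stated design:** 13.0 points unpooled, 13.1 pooled, about 13.5 with the t reference.

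**Sensitivity (unpooled).** ICC 0.01: 85%; 0.02: 79%; 0.05: 63%. For unequal shops with a mean of 23, the design effect is 1 + [(1 + CV²) × 23 − 1] × 0.03, where CV is the coefficient of variation of shop size. The documents give no CV. An assumed 0.4 gives a design effect of 1.77 and power of 70.1%; an assumed 0.65 gives 1.95 and 65.9%.

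**The case against.** The strongest objection is that no formula is named and the printed values are rounded. Assuming a constant coefficient of variation of shop rates, a recognised alternative, lifts power to about 76%. Taking the 29% relative reduction literally (p2 = 29.82%) as well gives about 77–78%. If the ICC of 0.03 is also a rounded 0.025 and the reduction is about 12.4 points, that model reaches about 81%. So a two-sided route to 80% exists, but it needs several favourable choices together, none of them in the documents. At the printed values the alternative model still stops near 76%, and the usual design-effect formula stays at or below about 78.5% even with both favourable roundings.

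A second argument is that 23 is called a minimum. The same sentence, however, fixes "15 barbershops for each intervention group (i.e., 30 clusters and 690 total participants", and 690/30 is exactly 23.

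A third is that the SAP model adjusts for baseline and covariates, which could raise power. That is possible, but the sample-size paragraph claims no such gain, so it does not explain the figure. It does mean that the corrected number describes the protocol's unadjusted calculation and not the SAP model.

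Finally, the SAP is dated August 2018 and written in the past tense, so no enrolment decision now depends on the 80%, and a confidence interval will show the precision achieved. This limits the practical consequence but leaves the figure wrong.

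**Conclusion.** The point holds. At the stated inputs the power is 72–73%, against a claimed 80%, and the type II error for the targeted effect is about 27–28%. The result rests on the usual design effect with the same ICC in both arms, equal shops of 23 and a normal reference. The main alternative variance model gives about 76%, still short of the claim, while a small-sample t reference gives 69–70%. The unequal-size figures depend on assumed CVs, and the conclusion does not need them.

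**What to change.** Restate the power sentence in *Study design and sample size*:

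- With 30 shops, 690 analysed men, an ICC of 0.03 and a two-tailed 5% test, power for a fall from 42% to 30% is about 73% (about 70% on 28 df). The difference detectable with 80% power is about 13 points (about 13.5 with t).
- Name the formula used. If the 80% came from a different input, state that input.
- Keep the minimum of 23 per shop, but say that the calculation assumes exactly 23 analysed men in every shop. Add that if the total stays at 690 and sizes vary so that some shops fall below 23, power is lower: about 70% to 66% for an assumed CV of 0.4 to 0.65.
- Optionally, show power by ICC: 85% at 0.01, 79% at 0.02, 63% at 0.05.

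The cost is wording only, with no added enrolment and no change to the per-shop minimum or the analysis. The only drawback is a less favourable stated power. With the study past data collection, the correction can stand as a dated note beside the existing paragraph, for use when the result is interpreted.
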